14.2.2 Total Plasma LOXO-292 Figures

Figure 14.2.2.1 Mean (SD) Total Plasma LOXO-292 Concentration-Time Profiles Following Administration of a Single Dose of 160 mg LOXO-292 to Subjects with Mild, Moderate, and Severe Renal Impairment and to Healthy Matched Control Subjects (Linear Scale) (Pharmacokinetic Population)

Figure 14.2.2.2 Mean Total Plasma LOXO-292 Concentration-Time Profiles Following Administration of a Single Dose of 160 mg LOXO-292 to Subjects with Mild, Moderate, and Severe Renal Impairment and to Healthy Matched Control Subjects (Linear Scale) (Pharmacokinetic Population)

Figure 14.2.2.3 Mean Total Plasma LOXO-292 Concentration-Time Profiles Following Administration of a Single Dose of 160 mg LOXO-292 to Subjects with Mild, Moderate, and Severe Renal Impairment and to Healthy Matched Control Subjects (Semi-Log Scale) (Pharmacokinetic Population)

Figure 14.2.2.4 Individual Total Plasma LOXO-292 AUC0-t Values, Geometric Means With Corresponding 95% CIs, and GMR With Corresponding 90% CIs Following Administration of a Single Dose of 160 mg LOXO-292 to Subjects with Mild, Moderate, and Severe Renal Impairment and to Healthy Matched Control Subjects (Pharmacokinetic Population)

Figure 14.2.2.5 Individual Total Plasma LOXO-292 AUC0-inf Values, Geometric Means With Corresponding 95% CIs, and GMR With Corresponding 90% CIs Following Administration of a Single Dose of 160 mg LOXO-292 to Subjects with Mild, Moderate, and Severe Renal Impairment and to Healthy Matched Control Subjects (Pharmacokinetic Population)

Figure 14.2.2.6 Individual Total Plasma LOXO-292 Cmax Values, Geometric Means With Corresponding 95% CIs, and GMR With Corresponding 90% CIs Following Administration of a Single Dose of 160 mg LOXO-292 to Subjects with Mild, Moderate, and Severe Renal Impairment and to Healthy Matched Control Subjects (Pharmacokinetic Population)

Note:

- Figures 14.2.2.4-6 are plots of AUCs and Cmax versus the cohorts.
- The x-axis will be the renal function and the y-axis will be the individual plasma PK parameters.

Figure 14.2.2.7 Scatter/Regression Plot of Individual Plasma LOXO-292 AUC0-t Versus eGFR

Figure 14.2.2.8 Scatter/Regression Plot of Individual Plasma LOXO-292 AUC0-inf Versus eGFR

Figure 14.2.2.9 Scatter/Regression Plot of Individual Plasma LOXO-292 Cmax Versus eGFR

Note:

- Figures 14.2.2.7-9 are scatter plots with regression lines.
- The x-axis will be the individual eGFR values and the y-axis will be the individual plasma PK parameters

Figure 14.2.2.10 Scatter/Regression Plot of Individual Plasma LOXO-292 AUC0-t Versus CLcr

Figure 14.2.2.11 Scatter/Regression Plot of Individual Plasma LOXO-292 AUC0-inf Versus CLcr

Figure 14.2.2.12 Scatter/Regression Plot of Individual Plasma LOXO-292 Cmax Versus CLcr

Note:

- Figures 14.2.2.10-12 are scatter plots with regression lines.
- The x-axis will be the individual CLcr values (found in the RFA dataset) and the y-axis will be the individual CLcr values

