12.1.3 Additional Requirements for Healthy Subjects

1. Healthy adult male and female subjects will be matched 1:1 to at least one specific subject in the renally impaired cohorts based upon age, BMI, and sex. The following criteria should be fulfilled:
 - Age must be within \pm 10 years of the matched subject(s)' age in the renally impaired cohort.
 - BMI must be within \pm 20% of the matched subject(s)' BMI in the renally impaired cohort.
2. Continuous non-smoker who has not used nicotine/tobacco containing products for at least 3 months prior to the first dosing and through EOT or ET.
3. Baseline eGFR \geq 90 mL/min/1.73 m² at Screening based on the MDRD equation as described in [Section 12.1.2](#) (Criterion 4). Based on the discretion of the PI or designee, a single assessment of actual creatinine clearance evaluated over a 24-hour urine collection may be used in place of the eGFR (based on the MDRD) equation for healthy subjects. Individual eGFR values recorded for each measurement contributing to the subject mean baseline value must fall within the specified eGFR range for a healthy matched subject (\geq 90 mL/min/1.73m²).
4. Medically healthy with no clinically significant medical history, physical examination, laboratory profiles, vital signs or ECGs, at Screening and at the time of Check-in (Day -1), as deemed by the PI or designee, and as confirmed by the Celerion Medical Monitor and the Sponsor.
5. Liver function tests (ALT and AST), serum (total and direct) bilirubin, amylase, and lipase must be within the upper limit of normal for the laboratory used by the CRU at Screening and Check-in (Day -1). Rechecks of the LFTs (ALT and AST), serum (total and direct) bilirubin, amylase and lipase will be permitted up to 2 times to confirm subject eligibility. Subjects may be eligible for participation in the study based on rechecked values if these values are within normal ranges and if the PI (or designee), with agreement from the Celerion Medical Monitor and the Sponsor, feels that the results are not clinically significant, and will not impact study conduct.

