- ** Baseline eGFR will be obtained by taking the mean of the eGFR obtained from Screening and from historical values within a 3-month period from Screening. If no historical measurement is available, a second Screening eGFR sample will be taken during the Screening period (\geq 14 days apart) and the mean of the two values will be used as the Baseline eGFR for cohort assignment. For healthy subjects, a single assessment of actual creatinine clearance computed over a 24 hour urine collection may be used in place of the eGFR (based on the MDRD equation), at the PI's discretion. Individual eGFR values recorded for each measurement contributing to the subject mean baseline value must fall within the specified eGFR ranges for each cohort (i.e., healthy, mild, moderate, and severe) to categorize subjects' renal impairment status.
- *** For subjects who are anuric, urine samples for urinalysis will not be collected.
- **** If urinalysis is positive for protein, blood, nitrite and/or leukocyte esterase, a microscopic examination (for red blood cells, white blood cells, bacteria, casts, and epithelial cells) will be performed.
- ***** Performed at Screening only.

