15.3.1.4 Additional Analysis

The relationship between LOXO-292 PK parameters (i.e., Cmax and AUC) and measures of renal function (such as eGFR and CLcr) may be explored using a linear regression approach or other methods, as indicated in the SAP.

The effect of covariates such as age, BMI, and gender may be investigated.

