6.7.3 Additional Analysis

The relationship between LOXO-292 PK parameters (i.e., Cmax and AUC, total and unbound) and measures of renal function (such as eGFR and CLcr) will be examined in an exploratory manner via a graphically linear regression approach. The PK parameters will be the dependent variable and show on y-axis and measurements for renal impairment will be independent variables and show on the x-axis. The regression equation with slope and intercept, the r-square, and the p-value for slope will be presented in the graphs as footnotes.

If data permits and judged necessary, an exploratory analysis will be performed to assess the relationship between LOXO-292 PK and renal impairment and the effect of covariates (age, BMI, and gender) using an appropriate approach.

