- The x-axis will be the individual eGFR values (found in the RFA dataset) and the y-axis will be the individual unbound plasma PK parameters

Figure 14.2.4.10 Scatter/Regression Plot of Individual Unbound Plasma LOXO-292 AUC_{0-t,u} Versus CL_{cr}

Figure 14.2.4.11 Scatter/Regression Plot of Individual Unbound Plasma LOXO-292 AUC_{0-inf,u} Versus CL_{cr}

Figure 14.2.4.12 Scatter/Regression Plot of Individual Unbound Plasma LOXO-292 C_{max,u} Versus CL_{cr}

Note:

- Figures 14.2.4.10-12 are scatter plots with regression lines.
- The x-axis will be the individual CL_{cr} values (found in the RFA dataset) and the y-axis will be the individual unbound plasma PK parameters

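### Do the six exploratory PK-versus-CLcr figures need changing because the SAP never says what CLcr is or which subjects have it?

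*SAP*

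**What the plan says.** Protocol 15.3.1.4 leaves the regression optional and refers the method to the SAP: "measures of renal function (such as eGFR and CLcr) may be explored using a linear regression approach". SAP 6.7.3 takes it up. The relation between PK parameters and "measures of renal function (such as eGFR and CLcr) will be examined in an exploratory manner", and on each plot "the r-square, and the p-value for slope will be presented in the graphs as footnotes", along with the equation.

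SAP 9.2 lists three CLcr figures for total drug (14.2.2.10 to 14.2.2.12) and three for unbound drug (14.2.4.10 to 14.2.4.12), covering AUC0-t, AUC0-inf and Cmax. The note to the total-drug set gives the source, "The x-axis will be the individual CLcr values (found in the RFA dataset", and then says "and the y-axis will be the individual CLcr values". The note to the unbound set reads "The x-axis will be the individual CL_{cr} values (found in the RFA dataset) and the y-axis will be the individual unbound plasma PK parameters". Six matching figures use eGFR instead.

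The measurement itself is described only for controls. Protocol 12.1.3 says that "a single assessment of actual creatinine clearance evaluated over a 24-hour urine collection may be used in place of the eGFR", at the investigator's discretion, and the creatinine footnote in Protocol 14.2.5 agrees: "For healthy subjects, a single assessment of actual creatinine clearance computed over a 24 hour urine collection may be used". The cohort table in SAP 3 repeats the provision. Under Protocol 12.1.2 and 12.2.2, subjects with renal impairment are classified and checked for stability by MDRD eGFR.

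**The concern.** A regression needs a defined regressor. For eGFR the documents give an equation, a unit and an averaging rule. For CLcr they give a dataset name.

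The one described measurement is confined to controls and is optional even there. Read literally, the six figures would plot exposure against creatinine clearance only in people with normal renal function, in a study meant to show what impaired function does to exposure. A flat line with a large p-value could then be taken for absence of a renal effect when it showed only absence of impaired subjects. Values for some impaired subjects, or a mixture of measured and calculated values, would also be hard to interpret if unlabelled. The note placing CLcr on both axes adds to the impression of figures that were not checked.

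**Working it through.** The documents state no sample size, power or decision rule for these regressions, so there is no planned figure to reproduce. The check has three parts.

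**1. Who could have a CLcr value**

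| Place | What it implies |
|---|---|
| Protocol 12.1.3 and 14.2.5; SAP 3 | One optional 24-hour collection, healthy controls only |
| Protocol 12.1.2 and 12.2.2 (current) | Impaired subjects: MDRD eGFR only |
| Protocol 12.2.2 in the original version and Amendment 1 (superseded) | Stability of impaired subjects could be judged on creatinine clearance or eGFR |
| Protocol 7, flow chart | Renal function assessed at Screening, no cohort restriction |
| SAP Appendix 16.2.4.4 shell | Creatinine-clearance date and result beside the eGFR columns, Safety Population, no cohort restriction |
| Protocol 14.1 and 14.2.5 | Serum creatinine, age, weight and sex collected in everyone, so a calculated value is possible |

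The first two rows suggest controls only. The other four leave room for impaired subjects without establishing that they have values. The statistical outputs supplied with the SAP contain the paired t-tests and the ANCOVA but no regression on either renal measure, so they do not settle the question.

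**2. The worst case in numbers**

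Assume RFA holds only the 24-hour values in controls.

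- The ANCOVA used 33 observations. The paired t-tests used 8 mild, 8 moderate and 7 severe subjects: 8 + 8 + 7 = 23, and 33 − 23 = 10 controls.
- Cross-check. The variance of a least-squares mean cannot be smaller than residual variance / n, so n ≥ residual variance / SE². For AUC0-t the residual variance is 0.1767:
  - mild: 0.1767 / 0.1512² = 7.73, so at least 8
  - moderate: 0.1767 / 0.1585² = 7.03, so at least 8
  - severe: 0.1767 / 0.1704² = 6.09, so at least 7
  - control: 0.1767 / 0.1364² = 9.50, so at least 10
  - These minima sum to 33, so the split is exactly 8, 8, 7 and 10.
- The figures would therefore show at most 10 / 33 = 30% of analysed subjects and 0 of 23 with impairment.
- The r-square needed for a two-sided slope p-value below 0.05 is t² / (df + t²), with df = n − 2:
  - n = 33: 0.12 (critical r = 0.344)
  - n = 10: 0.40 (critical r = 0.632)
  - n = 5, if only half the controls had the collection: 0.77 (critical r = 0.878)

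These thresholds follow from n alone. They describe how little a controls-only plot could show. They do not show that such a plot will be produced.

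**3. What each possible state of RFA would mean**

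- *Every cohort, one method.* The figures are sound and the loss is nil. Only a descriptive label is missing.
- *Controls only, or a mixture.* The gap is plain as soon as the values are listed by cohort in Appendix 16.2.4.4, and the figures can be labelled or left out. SAP 10 already says that shells may change.
- *A calculated CLcr for everyone.* It would use the same serum creatinine, age and sex as the MDRD equation, with weight as the main new input, and would largely repeat the eGFR figures.

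The y-axis note for Figures 14.2.2.10-12 is contradicted by the figure titles, by SAP 6.7.3 (PK parameters as the dependent variable) and by the note to the unbound figures. A variable plotted against itself would be noticed at once.

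**The case for a change.** The best argument for a change is that it is almost free. One sentence in SAP 6.7.3 giving the method, unit, time point and cohorts would remove the doubt. Listing columns that may turn out blank are no substitute for a definition, and the SAP commits to printing p-values on these plots. A controls-only regression printed without comment would be uninformative and could mislead.

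Most of this stands as description. No visible text defines CLcr, and the y-axis note is wrong. It is also fair that the eGFR figures are not wholly insulated: a control may qualify on creatinine clearance in place of eGFR, and the documents do not say which value that control contributes to the eGFR plots.

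What does not stand is the step to a defect in the analysis. The harm needs RFA to lack impaired subjects, which the documents do not show, and it needs the analyst to print the figures without noticing. The sentence asked for would record a fact about an existing dataset. It would not alter an estimand, a model or a population.

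**Conclusion.** No change to the plan. The gap is real but is a missing label in six exploratory figures, and the first step in resolving it is to look at the dataset, which any analyst must do to draw them. The axis note is a clerical slip that corrects itself from the figure titles.

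In the worst case the six figures rest on at most 10 of 33 subjects, none of them impaired, and say nothing about renal impairment. In the best case nothing is lost. The documents do not show which case applies. Either way, the comparisons that answer the primary objective (paired t-tests and ANCOVA) contain no CLcr term, and no decision rule depends on the slopes.

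This rests on three assumptions: that the appended outputs reflect the analysed population, that the CLcr regressions stay exploratory as SAP 6.7.3 states, and that the eGFR regressions remain the main graphical description of exposure against renal function. The last carries the reservation that some controls may have been classified by creatinine clearance.

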14.2.3 Unbound Plasma LOXO-292 Tables

Table 14.2.3.1	Concentrations of LOXO-292 (LOXO-292) (ng/mL), and Concentrations in the Buffer Chamber (LOXO-292 BC), Concentrations in the Plasma Chamber (LOXO-292 PC), % Recovery, and Fraction Unbound Obtained Following the Plasma Protein Binding Assay in Subjects with Mild Renal Impairment (Pharmacokinetic Population)
Table 14.2.3.2	Concentrations of LOXO-292 (LOXO-292) (ng/mL), and Concentrations in the Buffer Chamber (LOXO-292 BC), Concentrations in the Plasma Chamber (LOXO-292 PC), % Recovery, and Fraction Unbound Obtained Following the Plasma Protein Binding Assay in Subjects with Moderate Renal Impairment (Pharmacokinetic Population)
Table 14.2.3.3	Concentrations of LOXO-292 (LOXO-292) (ng/mL), and Concentrations in the Buffer Chamber (LOXO-292 BC), Concentrations in the Plasma Chamber (LOXO-292 PC), % Recovery, and Fraction Unbound Obtained Following the Plasma Protein Binding Assay in Subjects with Severe Renal Impairment (Pharmacokinetic Population)
Table 14.2.3.4	Concentrations of LOXO-292 (LOXO-292) (ng/mL), and Concentrations in the Buffer Chamber (LOXO-292 BC), Concentrations in the Plasma Chamber (LOXO-292 PC), % Recovery, and Fraction Unbound Obtained Following the Plasma Protein Binding Assay in Healthy Matched Control Subjects (Pharmacokinetic Population)
Table 14.2.3.5	Unbound Plasma LOXO-292 Concentrations (ng/mL) Following Administration of a Single Dose of 160 mg LOXO-292 to Subjects with Mild Renal Impairment (Pharmacokinetic Population)

Table 14.2.3.6	Unbound Plasma LOXO-292 Concentrations (ng/mL) Following Administration of a Single Dose of 160 mg LOXO-292 to Subjects with Moderate Renal Impairment (Pharmacokinetic Population)
Table 14.2.3.7	Unbound Plasma LOXO-292 Concentrations (ng/mL) Following Administration of a Single Dose of 160 mg LOXO-292 to Subjects with Severe Renal Impairment (Pharmacokinetic Population)
Table 14.2.3.8	Unbound Plasma LOXO-292 Concentrations (ng/mL) Following Administration of a Single Dose of 160 mg LOXO-292 to Healthy Matched Control Subjects (Pharmacokinetic Population)
Table 14.2.3.9	Unbound Plasma LOXO-292 Pharmacokinetic Parameters Following Administration of a Single Dose of 160 mg LOXO-292 to Subjects with Mild Renal Impairment (Pharmacokinetic Population)
Table 14.2.3.10	Unbound Plasma LOXO-292 Pharmacokinetic Parameters Following Administration of a Single Dose of 160 mg LOXO-292 to Subjects with Moderate Renal Impairment (Pharmacokinetic Population)
Table 14.2.3.11	Unbound Plasma LOXO-292 Pharmacokinetic Parameters Following Administration of a Single Dose of 160 mg LOXO-292 to Subjects with Severe Renal Impairment (Pharmacokinetic Population)
Table 14.2.3.12	Unbound Plasma LOXO-292 Pharmacokinetic Parameters Following Administration of a Single Dose of 160 mg LOXO-292 to Healthy Matched Control Subjects (Pharmacokinetic Population)
Table 14.2.3.13	Intervals (Hours) Used for Determination of Unbound Plasma LOXO-292 Kel Values Following Administration of a Single Dose of 160 mg LOXO-292 to Subjects with Mild, Moderate, and Severe Renal Impairment and to Healthy Matched Control Subjects (Pharmacokinetic Population)
Table 14.2.3.14	Statistical Comparisons of Unbound Plasma LOXO-292 Pharmacokinetic Parameters Following Administration of a Single Dose of 160 mg LOXO 292 to Subjects with Mild

Renal Impairment Versus Healthy Matched Control
Subjects (Paired T-Test) (Pharmacokinetic Population)

Table 14.2.3.15 Statistical Comparisons of Unbound Plasma LOXO-292 Pharmacokinetic Parameters Following Administration of a Single Dose of 160 mg LOXO 292 to Subjects with Moderate Renal Impairment Versus Healthy Matched Control Subjects (Paired T-Test) (Pharmacokinetic Population)

Table 14.2.3.16 Statistical Comparisons of Unbound Plasma LOXO-292 Pharmacokinetic Parameters Following Administration of a Single Dose of 160 mg LOXO 292 to Subjects with Severe Renal Impairment Versus Healthy Matched Control Subjects (Paired T-Test) (Pharmacokinetic Population)

Table 14.2.3.17 Statistical Comparisons of Unbound Plasma LOXO-292 Pharmacokinetic Parameters Following Administration of a Single Dose of 160 mg LOXO 292 to Subjects with Mild Renal Impairment Versus Healthy Matched Control Subjects (Pharmacokinetic Population)

Table 14.2.3.18 Statistical Comparisons of Unbound Plasma LOXO-292 Pharmacokinetic Parameters Following Administration of a Single Dose of 160 mg LOXO 292 to Subjects with Moderate Renal Impairment Versus Healthy Matched Control Subjects (Pharmacokinetic Population)

Table 14.2.3.19 Statistical Comparisons of Unbound Plasma LOXO-292 Pharmacokinetic Parameters Following Administration of a Single Dose of 160 mg LOXO 292 to Subjects with Severe Renal Impairment Versus Healthy Matched Control Subjects (Pharmacokinetic Population)

14.2.4 Unbound Plasma LOXO-292 Figures

Figure 14.2.4.1 Mean (SD) Unbound Plasma LOXO-292 Concentration-Time Profiles Following Administration of a Single Dose of 160 mg LOXO-292 to Subjects with Mild, Moderate, and Severe Renal Impairment and to Healthy Matched Control Subjects (Linear Scale) (Pharmacokinetic Population)

Figure 14.2.4.2 Mean Unbound Plasma LOXO-292 Concentration-Time Profiles Following Administration of a Single Dose of 160 mg LOXO-292 to Subjects with Mild, Moderate, and Severe Renal Impairment and to Healthy Matched Control Subjects (Linear Scale) (Pharmacokinetic Population)

Figure 14.2.4.3 Mean Unbound Plasma LOXO-292 Concentration-Time Profiles Following Administration of a Single Dose of 160 mg LOXO-292 to Subjects with Mild, Moderate, and Severe Renal Impairment and to Healthy Matched Control Subjects (Semi-Log Scale) (Pharmacokinetic Population)

Figure 14.2.4.4 Individual Unbound Plasma LOXO-292 AUC_{0-t,u} Values, Geometric Means With Corresponding 95% CIs, and GMR With Corresponding 90% CIs Following Administration of a Single Dose of 160 mg LOXO 292 to Subjects with Mild, Moderate, and Severe Renal Impairment and to Healthy Matched Control Subjects (Pharmacokinetic Population)

Figure 14.2.4.5 Individual Unbound Plasma LOXO-292 AUC_{0-inf,u} Values, Geometric Means With Corresponding 95% CIs, and GMR With Corresponding 90% CIs Following Administration of a Single Dose of 160 mg LOXO 292 to Subjects with Mild, Moderate, and Severe Renal Impairment and to Healthy Matched Control Subjects (Pharmacokinetic Population)

Figure 14.2.4.6 Individual Unbound Plasma LOXO-292 C_{max,u} Values, Geometric Means With Corresponding 95% CIs, and GMR With Corresponding 90% CIs Following Administration of a Single Dose of 160 mg LOXO 292 to Subjects with Mild, Moderate, and Severe Renal Impairment and to Healthy Matched Control Subjects (Pharmacokinetic Population)

Note:

- Figures 14.2.4.4-6 are plot of AUCs and C_{max} versus the cohorts.
- The x-axis will be the renal function and the y-axis will be the individual unbound plasma PK parameters.

Figure 14.2.4.7 Scatter/Regression Plot of Individual Unbound Plasma LOXO-292 AUC_{0-t,u} Versus eGFR

Figure 14.2.4.8 Scatter/Regression Plot of Individual Unbound Plasma LOXO-292 AUC_{0-inf,u} Versus eGFR

Figure 14.2.4.9 Scatter/Regression Plot of Individual Unbound Plasma LOXO-292 C_{max,u} Versus eGFR

Note:

- Figures 14.2.4.7-9 are scatter plots with regression lines.
- The x-axis will be the individual eGFR values (found in the RFA dataset) and the y-axis will be the individual unbound plasma PK parameters

Figure 14.2.4.10 Scatter/Regression Plot of Individual Unbound Plasma LOXO-292 AUC_{0-t,u} Versus CL_{cr}

Figure 14.2.4.11 Scatter/Regression Plot of Individual Unbound Plasma LOXO-292 AUC_{0-inf,u} Versus CL_{cr}

Figure 14.2.4.12 Scatter/Regression Plot of Individual Unbound Plasma LOXO-292 C_{max,u} Versus CL_{cr}

Note:

- Figures 14.2.4.10-12 are scatter plots with regression lines.
- The x-axis will be the individual CL_{cr} values (found in the RFA dataset) and the y-axis will be the individual unbound plasma PK parameters

